**8.1 Inclusion Criteria****Parts A and B**

Subjects who meet all of the following inclusion criteria will be eligible for Part A and Part B.

1. Subject (or his or her legally appointed and authorized representative) will sign and date an informed consent form (ICF), and an assent form.
2. Subjects (males and/or females), 6 through 11 years of age, inclusive, on the date of informed consent.
3. Subjects who weigh  $\geq 15$  kg without shoes at the Screening Visit.
4. Confirmed diagnosis of CF as determined by the investigator.
5. Subjects who are homozygous for *F508del* (F/F genotype) or heterozygous for *F508del* and an MF mutation that is not responsive to IVA and TEZ/IVA (F/MF genotypes; Appendix A).

- Genotype should be confirmed at the Screening Visit. This assessment does not need to be repeated for confirmed subjects in Part A who wish to participate in Part B.
  - If the screening *CFTR* genotype result is not received before the first dose of study drug, a previous *CFTR* genotype laboratory report may be used to establish eligibility.
  - Subjects who have been enrolled and whose screening genotype does not confirm study eligibility must be discontinued from the study (Section 9.9).
6. Subjects with FEV1 ≥40% of predicted normal for age, sex, and height using equations of the Global Lung Function Initiative (GLI) at the Screening Visit (Section 11.4.1). Spirometry measurements used to confirm eligibility must meet American Thoracic Society/European Respiratory Society criteria for acceptability and repeatability, as judged by the investigator.
  7. Subjects with stable CF disease at the start of the Treatment Period as deemed by the investigator.
  8. Subjects who are willing to remain on a stable CF medication regimen (other than *CFTR* modulators) through Day 15 (**Part A**) or through Week 24 (**Part B**) or, if applicable, through the Safety Follow-up Visit.
  9. Subjects who are able to swallow tablets.
  10. Female subjects must have a negative serum pregnancy test at the Screening Visit.
  11. Subjects of childbearing potential and who are sexually active must meet the contraception requirements outlined in Section 11.5.6.1.

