### 9.2 Method of Assigning Subjects to Treatment Groups

This is an open-label study. Randomization is not required because all subjects will be treated identically. An interactive web response system (IWRS) will be used to dispense dosage based on subject weight at Day 1.

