7.1 Overall Design

This is a Phase 3, 2-part (Parts A and B), multicenter study evaluating the PK, safety, and tolerability of ELX/TEZ/IVA TC therapy in CF (F/F and F/MF genotypes) subjects 6 through 11 years of age (inclusive).

Part A

A schematic of the study design for Part A is provided in Figure 7-1. Approximately 12 subjects (F/F or F/MF genotypes) are planned for enrollment. During the Treatment Period, subjects will be administered ELX/TEZ/IVA for approximately 15 days. A review of safety, tolerability, and available PK data will be completed by an internal Vertex team after Part A to confirm or adjust the dose(s) chosen for Part B. Additional subjects may be enrolled as needed in Part A, based on emerging PK data, to confirm the dose(s) for Part B. Subjects who participate in Part A may participate in Part B.

Figure 7-1 Part A Study Design

IVA: ivacaftor; n: number of subjects; TEZ: tezacaftor

^a VX-445/TEZ/IVA will be administered from Day 1 through Day 15. On Day 15, only the morning dose will be administered.

[figure not shown]
Part B

A schematic of the study design for Part B is provided in Figure 7-2. Part B will initiate after completion of the internal Vertex team's review of available data in Part A that will confirm or adjust the dose(s) to be evaluated in Part B. Approximately 56 subjects (F/F or F/MF genotypes) are planned for enrollment to ensure approximately 45 subjects complete Part B. Approximately 25 subjects with F/MF genotypes and approximately 20 subjects with F/F genotypes are targeted for enrollment in Part B. During the Treatment Period, subjects will be administered ELX/TEZ/IVA for approximately 24 weeks.

Subjects who complete the Part B Treatment Period and have not permanently discontinued study drug will be offered the opportunity to enroll in an optional open-label extension safety study (enrollment will be based on the eligibility criteria specified within the Open-label Extension Safety Study protocol).

Figure 7-2 Part B Study Design

IVA: ivacaftor; TEZ: tezacaftor

- ^a The Safety Follow-up Visit is scheduled to occur 4 weeks (± 7 days) after the last dose. This visit is not required for subjects who enroll in an optional open-label extension safety study within 28 days of the last dose.

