7.2 Sample Size and Power

Part A

Approximately 12 subjects will be enrolled in Part A. Sample size calculations were determined based on ELX PK, using noncompartmental analysis (NCA)-based parameters, such as clearance and volume of distribution. Based on the variability observed in adults, data from 12 subjects will allow

80% power to target a 95% CI within 60% and 140% of the geometric mean estimate of clearance for ELX.

Part B

The planned enrollment is approximately 56 subjects. Approximately 45 subjects are expected to complete Part B. Incidence of AEs is a safety endpoint. Table 7-2 presents estimates of the probability for observing at least 1 subject with an AE for the given incidence (θ) and sample size. The study will have at least 90% chance of observing an AE in at least 1 subject if the true incidence rate is 5%; and a >95% chance of observing an AE in at least 1 subject if the true incidence rate is 10%. The probabilities have been calculated by assuming a binomial distribution for the number of AEs using SAS.

Table 7-2 Probability of Observing At Least 1 Subject with an AE in the Study if the AE Incidence (θ) is 5% and 10%

Sample Size	$\theta = 5\%$	$\theta = 10\%$
45	90.0%	99.1%
50	92.3%	99.5%

AE: adverse event

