9.3.2.2.2 Analysis Method

Absolute change in ppFEV₁ from baseline through Week 24:

Absolute change from baseline in ppFEV₁ will be analyzed using a mixed-effects model for repeated measures (MMRM) approach based on the FAS. The MMRM will be used to estimate the within-group mean absolute change in ppFEV₁ through Week 24. The model will include absolute change from baseline in ppFEV₁ (including all measurements up to Week 24 [inclusive], both on-treatment measurements and measurements after treatment discontinuation) as the dependent variable, and visit as the fixed effect, with baseline ppFEV₁ value and genotype group (F/F vs. F/MF) as covariates. The model will be estimated using restricted maximum likelihood. Denominator degrees of freedom for the *F*-test of fixed effects will be estimated using the Kenward-Roger approximation². An unstructured covariance structure will be used to model the within-subject errors. If the model estimation does not converge, a compound symmetry covariance structure will be used instead. Conditional on the observed data and covariates, missing data will be assumed to be missing at random; consequently, no imputation of missing data will be performed.

The results obtained from the model will be the average treatment effect through Week 24. Note that the Day 15 Visit will not be included in the estimation of the average treatment effect through Week 24 as the treatment effect is not expected to reach the steady state at Day 15. The estimated mean change from baseline in ppFEV₁ through Week 24, along with the corresponding 2-sided 95% confidence interval (CI) and *P*-value will be provided. The treatment effect at each post-baseline visit with 95% CI, obtained from the model, will be provided as well.

The analysis will be conducted with the clinic spirometry data only. An additional analysis may also be performed to include pooled spirometry data obtained in clinic and by Air Next Spirometer, if the Air Next Spirometry data are assessed to be reasonably consistent with clinic spirometry data.

Absolute change in sweat chloride from baseline through Week 24:

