Analysis of this PD variable will be based on an MMRM similar to the analysis of the absolute change in ppFEV₁ from baseline through Week 24 with the baseline sweat chloride included as a covariate instead of baseline ppFEV₁. Data obtained from Day 15, Week 4, Week 12, and Week 24 Visits will be included in the model. However, Day 15 Visit will not be included in the estimation of the average treatment effect through Week 24 as the treatment effect is not expected to reach the steady state at Day 15.

Absolute change in the CFQ-R respiratory domain score from baseline through Week 24:

Analysis of this domain (child's version) will be based on an MMRM similar to the analysis of the absolute change in ppFEV₁ from baseline through Week 24 with the baseline CFQ-R respiratory domain score (child's version) included as a covariate instead of baseline ppFEV₁. Data obtained from Week 4, Week 8, Week 12, Week 16, and Week 24 Visits will be included in the model and all of these visits will be included in the estimation of the average treatment effect through Week 24. The analysis will include only the clinic assessed CFQ-R RD score. An additional analysis may be performed to include CFQ-R RD score assessed at clinic and at home, if the home assessed data are consistent with the clinic assessed data.

Absolute change in BMI and BMI-for-age z-score from baseline at Week 24;

Absolute change in weight and weight-for-age z-score from baseline at Week 24;

Absolute change in height and height-for-age z-score from baseline at Week 24:

Analysis of these variables will be based on an MMRM similar to the analysis of the absolute change in ppFEV₁ from baseline through Week 24 with the corresponding baseline included as a covariate instead of baseline ppFEV₁. Data obtained from Day 15, Week 4, Week 8, Week 12, Week 16, and Week 24 Visits will be included in the model.

Drug acceptability assessment using Modified Facial Hedonic Scale:

Analysis of this variable will be based on descriptive statistics. The number and percentage (based on the FAS) of subjects in each category will be summarized for each question at all scheduled visit. The analysis will include only the data assessed at clinic. An additional analysis may be performed to include the data assessed at clinic and at home, if the home assessed data are consistent with the clinic assessed data.

Number of PEx and CF-related hospitalizations through Week 24:

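### Raw height, weight and BMI change in growing children are modelled against zero change as if it were a treatment effect, although ordinary growth alone moves height, and usually weight, clearly off zero

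*SAP*

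**What the plan says.** Part B is uncontrolled: "This is an open-label study. Randomization is not required because all subjects will be treated identically" (Protocol 9.2). Eligible children are "6 through 11 years of age, inclusive, on the date of informed consent" (Protocol 8.1), and "subjects will be administered ELX/TEZ/IVA for approximately 24 weeks" (SAP 7.1).

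The secondary endpoints include raw BMI, weight and height change at Week 24, each paired with its z-score (SAP 6.2; Protocol 7.2), for example "Absolute change in height and height-for-age z-score from baseline at Week 24" (SAP 9.3.2.2.2). For all six the SAP states: "Analysis of these variables will be based on an MMRM similar to the analysis of the absolute change in" ppFEV1, with the variable's own baseline as covariate (SAP 9.3.2.2.2). Protocol 12.3.3.2 specifies the same.

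The ppFEV1 model estimates a within-group mean change. Its main output, the average through Week 24, is called a treatment effect and comes with a 2-sided 95% CI and a P value. For single visits: "The treatment effect at each post-baseline visit with 95% CI, obtained from the model, will be provided as well" (SAP 9.3.2.2.2). SAP 9.3.2 adds that P values provided for secondary endpoints are nominal, without multiplicity adjustment.

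The z-scores are adjusted for age and sex with CDC growth charts (SAP 9.3.2.2.1); the raw measures are not. Neither document gives an expected-growth reference for the raw measures or warns that their change includes growth.

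**The concern.** The ppFEV1 model suits ppFEV1 because that variable is a ratio to a predicted value that already depends on age and height. Expected growth has been taken out, so zero change is a reasonable reference. Raw height and weight have no such adjustment. Children of this age grow over 24 weeks with or without study drug, and no control arm shows by how much.

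Taken over unchanged, the model compares raw height and weight with a value that would not be expected even if the drug did nothing. An interval that excludes zero, reported as a treatment effect, then invites the reader to credit the drug with ordinary growth. Nominal status does not cure this: it concerns multiplicity, whereas the difficulty here is the reference value.

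**Working it through.** **The plan's own figures.** "The planned enrollment is approximately 56 subjects" and "Approximately 45 subjects are expected to complete Part B" (SAP 7.2). The only Part B sample-size figures are probabilities of seeing at least one subject with an AE, 1 − (1 − θ)ⁿ. For n = 45: 1 − 0.95⁴⁵ = 0.9006 and 1 − 0.90⁴⁵ = 0.9913. For n = 50: 0.9231 and 0.9948. These reproduce SAP Table 7-2. No effect size, SD or power is given for growth, so nothing in the sample-size section bears on this point.

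**Method.** I approximate the Week 24 within-group contrast by a one-sample t: t = mean change / (SD / √n), two-sided, df = n − 3, n = 45 (√45 = 6.708). Drug effect is set to zero throughout. Duration is 168 / 365.25 = 0.46 year.

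**Assumptions, not in the documents.** Height gain 4 to 7 cm/year, SD of change 0.7 to 2.0 cm. Weight gain 1.5 to 3.5 kg/year, SD 0.8 to 2.0 kg. BMI drift 0 to 0.7 kg/m² per year, SD 0.5 to 1.0.

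| Measure | Case | Mean change in 24 weeks | SD | t | P |
|---|---|---|---|---|---|
| Height (cm) | least extreme | 4 × 0.46 = 1.84 | 2.0 | 1.84 × 6.708 / 2.0 = 6.17 | 2 × 10⁻⁷ |
| | mid | 5.5 × 0.46 = 2.53 | 1.0 | 16.97 | 2 × 10⁻²⁰ |
| | most extreme | 7 × 0.46 = 3.22 | 0.7 | 30.9 | 2 × 10⁻³⁰ |
| Weight (kg) | least extreme | 1.5 × 0.46 = 0.69 | 2.0 | 0.69 × 6.708 / 2.0 = 2.31 | 0.026 |
| | mid | 2.5 × 0.46 = 1.15 | 1.2 | 6.43 | 1 × 10⁻⁷ |
| | most extreme | 3.5 × 0.46 = 1.61 | 0.8 | 13.5 | 7 × 10⁻¹⁷ |
| BMI (kg/m²) | least extreme | 0 | any | 0 | 1.0 |
| | mid | 0.4 × 0.46 = 0.184 | 0.7 | 1.76 | 0.085 |
| | most extreme | 0.7 × 0.46 = 0.322 | 0.5 | 4.32 | 9 × 10⁻⁵ |

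**Thresholds.** With n = 45, P < 0.05 needs mean/SD of at least 0.30, and P < 0.0001 needs at least 0.64. From growth alone, height gives 0.92 to 4.6, weight 0.34 to 2.0 and BMI 0 to 0.64.

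**Why BMI differs.** The SAP defines BMI as weight over height squared, so height gain offsets weight gain. Take an assumed child of 26 kg and 128 cm: 26 / 1.28² = 15.87. After gaining 1.15 kg and 2.53 cm: 27.15 / 1.3053² = 15.94, a change of +0.07. Across the assumed height and weight gains, the change for that child runs from −0.37 to +0.51, so even the sign is not fixed. In the mid case the chance of P < 0.05 is about 41%, against 5% for a z-score whose untreated mean change is zero.

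**All 56 subjects.** The mid-case P values become 3 × 10⁻²⁵ (height), 2 × 10⁻⁹ (weight) and 0.054 (BMI). The pattern is the same.

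**The case against.** The strongest reply has four parts.

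- **The P value is not stated for these endpoints.** The growth endpoints are at a single visit. The ppFEV1 text attaches its P value to the average through Week 24 and names only a CI for each visit; the later paragraph on longitudinal profiles likewise names an LS mean, SE and 95% CI. This stands. A Week 24 P value is inferred from the word similar together with the general sentence in SAP 9.3.2. The concern survives in reduced form, because the visit-level estimate is itself labelled a treatment effect, and a CI for raw height that excludes zero under that label misleads in the same way.
- **The label is inherited.** The growth paragraph does not use it, and nothing in the documents says that growth will be attributed to the drug. That also stands. The risk comes from reusing the ppFEV1 specification without adapting it.
- **The safeguard is already planned.** Every raw measure has its z-score beside it, and descriptive summaries of raw values and change are planned too. This is true and makes the fix cheap, but it does not make zero the right reference for the raw measures.
- **Little depends on it.** The primary endpoint is safety, the efficacy P values are nominal, and no decision rule or sample size uses them. This stands and limits the point to a minor one.

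A reader might infer that all three raw measures must give a minute P value whatever the drug does. The documents do not support that: the BMI formula lets height gain cancel weight gain, and weight reaches only P = 0.026 at the slow-growth, high-SD end. A reader might also infer that the z-scores have a secure null of zero. Nothing in the documents shows that untreated children with CF hold a constant z-score over 24 weeks.

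**Conclusion.** The point holds, as a minor one. For raw height, zero change is not a no-effect value, and growth alone gives P of about 2 × 10⁻⁷ or smaller in every case tried. For raw weight the same holds in most cases: P runs from 0.026 to 7 × 10⁻¹⁷, mid case about 1 × 10⁻⁷. Raw BMI is less affected (mid case P about 0.09), but zero is not secure there either.

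These sizes rest on growth rates and SDs that I assumed, on 45 completers, and on a one-sample t standing in for the MMRM contrast. The direction for height does not depend on where in the assumed range one sits. That a Week 24 P value will be produced is a reasonable reading of the SAP, not something it states.

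**What to change.** In SAP 9.3.2.2.2, separate the raw growth measures from the z-scores:

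- For raw height, weight and BMI, report descriptive statistics and, if wanted, the LS mean change with 95% CI. Give no P value and do not call the result a treatment effect. Keeping the LS mean stays in line with the MMRM named in Protocol 12.3.3.2.
- Base growth inference on the height, weight and BMI z-scores already planned.
- Add one sentence saying that the z-scores remove expected growth for age and sex but, without a control arm, do not by themselves isolate a drug effect.

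The cost is SAP wording and up to three fewer nominal P values. No endpoint is lost: descriptive summaries are already planned for Part B, and SAP 9.3.1.3 treats the same measures descriptively in Part A.

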#### **11.4.6.2 Hospitalization for CF**

Subjects will be queried about planned and unplanned hospitalizations lasting  $\geq 24$  hours that occurred during the study. The dates of hospitalizations and the reasons for hospitalizations will be documented.

For any hospitalization (planned and unplanned), the procedures for safety reporting should also be followed.

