6.2 Secondary Endpoints

Part A

[figure not shown]
- PK parameters of ELX, TEZ and IVA metabolites, including C_{max} , C_{trough} , and $AUC_{0-\tau}$
- Safety and tolerability as determined by AEs, clinical laboratory values, standard 12-lead ECGs, vital signs and pulse oximetry

Part B

- Absolute change in percent predicted forced expiratory volume in 1 second (ppFEV₁) from baseline through Week 24
- Absolute change in sweat chloride (SwCl) from baseline through Week 24
- Absolute change in Cystic Fibrosis Questionnaire-Revised (CFQ-R) respiratory domain score from baseline through Week 24
- Absolute change in body mass index (BMI) and BMI-for-age z-score from baseline at Week 24
- Absolute change in weight and weight-for-age z-score from baseline at Week 24
- Absolute change in height and height-for-age z-score from baseline at Week 24
- Drug acceptability assessment using Modified Facial Hedonic Scale
- Number of pulmonary exacerbations (PEX) and CF-related hospitalizations through Week 24

- PK parameters of ELX, TEZ, IVA, and relevant metabolites
- Absolute change in lung clearance index_{2.5} (LCI_{2.5}) from baseline through Week 24

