Height z-score and Weight z-score: the height z-score and weight z-score, adjusted for age and sex, will be referred to as weight-for-age z-score (weight z-score) and height-for-age z-score (height z-score). The weight z-score and height z-score will be calculated by using Centers for Disease Control and Prevention (CDC) growth charts⁸, with the age (in months) used for the calculation defined in [Appendix A](#).

Modified Facial Hedonic Scale: refer to Section 11.3.1 of the CSP for details.

Pulmonary exacerbation (PEX): A PEX is defined as a new or changed antibiotic therapy (intravenous [IV], inhaled, or oral) for any 4 or more of the following signs/symptoms:

- Change in sputum
- New or increased hemoptysis
- Increased cough
- Increased dyspnea
- Malaise, fatigue, or lethargy
- Temperature above 38°C (equivalent to approximately 100.4°F)
- Anorexia or weight loss
- Sinus pain or tenderness
- Change in sinus discharge
- Change in physical examination (PE) of the chest
- Decrease in pulmonary function by 10%
- Radiographic changes indicative of pulmonary infection

The **PEX analysis period** will include the time from the first dose date of study drug until the last efficacy assessment, which may be collected up to the Week 24 Visit or the earlier of Day 169 and the end of study participation if the subject does not have the Week 24 Visit.

The number of PEX through Week 24 is then defined as the total number of PEX during the PEX analysis period.

Lung clearance index (LCI): the LCI assessments are derived from N₂-multiple-breath washout (MBW) testing. Each MBW will be performed in multiple replicates for each visit and the final LCI value will be calculated from the technically acceptable washout replicates as graded and determined by a central reader. The following algorithm is used to derive the LCI values at each visit based on the multiple replicates:

- When there is only one acceptable replicate at the visit, the LCI values will not be calculated. The assessment for that subject at the corresponding visit will be missing.
- When there are 2 or more acceptable replicates at the visit, the mean of the values for the acceptable replicates will be calculated as the LCI value at the corresponding visit.

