The analysis period for these variables will be the same as the PEx analysis period.

PEx will be summarized as described below:

- Number of events:
 - Number of PEx
 - Number of PEx requiring hospitalizations
 - Number of PEx requiring IV antibiotic therapy
 - Number of PEx requiring hospitalization or IV antibiotic therapy
- Duration of events:
 - Number of days with PEx
 - Number of days with PEx requiring hospitalizations
 - Number of days with PEx requiring IV antibiotic therapy
 - Number of days with PEx requiring hospitalization or IV antibiotic therapy

CF-related hospitalizations will be summarized as described below:

- Number of events:
 - Number of planned hospitalizations for CF (i.e., antibiotic therapy)
 - Number of unplanned hospitalizations for reasons other than antibiotic therapy for sinopulmonary signs/symptoms
- Duration of events:
 - Number of days of planned hospitalizations for CF (i.e., antibiotic therapy)
 - Number of days of unplanned hospitalizations for reasons other than antibiotic therapy for sinopulmonary signs/symptoms

For number of events variables, subjects with multiple defined events during the PEx analysis period will be counted multiple times. The annualized duration of events for each subject will be the total number of days with the defined events times 48 weeks divided by the total number of weeks on study up to the end of the PEx analysis period.

Absolute change in LCI_{2.5} from baseline through Week 24:

Analysis of this variable will be based on an MMRM similar to the analysis of the absolute change in ppFEV₁ from baseline through Week 24 with the baseline LCI_{2.5} included as a covariate instead of baseline ppFEV₁. Data obtained from Day 15, Week 4, Week 12, and Week 24 Visits will be included in the model. However, Day 15 Visit will not be included in the estimation of the average treatment effect through Week 24 as the treatment effect is not expected to reach the steady state at Day 15.

[figure not shown]
To better assess the longitudinal profile of the efficacy and pharmacodynamics assessments with repeated measures up to Week 24, the LS mean (SE) of the change from baseline at each post-baseline visit along with the 95% CI will be estimated from the corresponding MMRM. The LS mean (SE) at each visit will also be plotted. In addition, the post-baseline raw values and the absolute

[figure not shown]

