⁴ For safety assessment, Safety Follow-up analysis visit will be based on nominal Safety Follow-up visit. If a subject doesn't have a nominal Safety Follow-up visit but has an ETT visit with study day >29 for Part A and >183 for Part B, then the ETT visit will be mapped into Safety Follow-up analysis visit.

⁵ For efficacy analysis of Part B, if there are assessments with study days > 183, the nominal Safety Follow-up visit will be mapped to the Safety Follow-up visit. If there is only ETT assessment with study day > 183, the ETT visit will be mapped to the Safety Follow-up visit.

Derived Variables:

1. Age (in years) at first dose date and nominal visit (for demographics, listing and the calculation of [percent] predicted spirometry variables):

Obtain the age at informed consent/assent (in days) in "yy, mm" format (e.g., 24 years, 6 months) from the Vital Signs (VS) page at the Screening Visit, and add 0.5 month to convert to days.

Obtain the informed consent/assent date.

Then age (in years) at first dose or nominal visit = [(first dose date or nominal visit date – informed consent/assent date) in days + age at informed consent/assent (in days)]/365.25.

2. Age (in months) at nominal visit (for use in calculation of BMI, weight z-score and height z-score, as applicable):

Obtain the age at informed consent/assent (in months) in "yy, mm" format (e.g., 24 years, 6 months) from Vital Signs (VS) page at the Screening Visit.

Obtain the informed consent/assent date.

Then age (in months) at nominal visit = integer part of {[age at informed consent/assent (in months) + 0.5 + diff (first dose date or nominal visit date, informed consent/assent date) in months]} + 0.5.

3. Missing first dose date or last dose date

If the first dose date is missing, use Day 1 visit date to impute.

If the last dose date is missing or partial date is reported, the last dose date will be imputed based on, in descending order priority, the Early Treatment Termination (ETT) visit date, last visit date before the Safety Follow-up, or the last study drug administration date from EX SDTM domain, as appropriate. The imputation algorithm will ensure the imputed last dose date does not exceed the study participation end date.

4. Sweat Chloride:

Non-missing sweat chloride concentrations from the left arm and right arm with assessment end date/time for a given arm up to 30 minutes after first dose time in treatment period will be considered for baseline.

5. Electrocardiogram:

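### The planned tables cannot give the number of CF-related hospitalizations: some unplanned antibiotic admissions fall in no row and there is no total. The annualized durations use a 48-week year.

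*SAP*

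**What the plan says.** SAP 6.2 lists among the Part B secondary endpoints "Number of pulmonary exacerbations (PEX) and CF-related hospitalizations through Week 24"; protocol 7.2 has the same endpoint. Protocol 12.3.3.2 says only that these numbers will be summarized, so the counting rules come from SAP 9.3.2.2.2.

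That section gives two event rows for CF-related hospitalizations:

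- "Number of planned hospitalizations for CF (i.e., antibiotic therapy" (the parenthesis closes there), and
- "Number of unplanned hospitalizations for reasons other than antibiotic therapy for sinopulmonary signs/symptoms".

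The same two categories are repeated for days. Separate PEx rows count exacerbations that required hospitalization, IV antibiotics, or either. Under SAP 9.3.2.2.1 a PEx is new or changed antibiotic therapy "for any 4 or more of the following signs/symptoms", and 12 signs follow.

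On data collection, protocol 11.4.6.2 has subjects asked about planned and unplanned stays of at least 24 hours, and says "The dates of hospitalizations and the reasons for hospitalizations will be documented".

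For durations, SAP 9.3.2.2.2 defines the annualized value for each subject as "the total number of days with the defined events times 48 weeks divided by the total number of weeks on study", counted to the end of the PEx analysis period.

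**The concern.** Two rows that are meant to describe CF-related hospitalizations should between them cover every such admission, or a total should be given. Here the planned row is limited to antibiotics, while the unplanned row excludes sinopulmonary antibiotics. A child admitted unplanned for such antibiotics is therefore outside both rows. The PEx rows recover that admission only if the 4-sign threshold is met. If the SAP is followed exactly, the number named in the endpoint is not among the outputs and cannot be rebuilt from them.

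The second point is one of scale. A table headed as annualized will be read as per calendar year, and 48 weeks is about four weeks short of that. The SAP gives no reason for the choice.

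**Working it through.** **Coverage.** Each type of admission is assigned to the rows of SAP 9.3.2.2.2 as worded, using the PEx threshold of SAP 9.3.2.2.1.

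| Admission | Reason | Signs | Row(s) |
|---|---|---|---|
| Unplanned | Sinopulmonary antibiotics | 4 or more | PEx requiring hospitalization |
| Unplanned | Sinopulmonary antibiotics | fewer than 4 | none |
| Unplanned | Other | – | Unplanned row |
| Planned | Antibiotics | 4 or more | Planned row and PEx requiring hospitalization |
| Planned | Antibiotics | fewer than 4 | Planned row |
| Planned | Other | – | none, if the parenthesis in the planned row is read literally |

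Three things follow.

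- The two CF-related rows omit all unplanned admissions for sinopulmonary antibiotics. Those with 4 or more signs are recovered in the PEx rows; those with fewer are not shown for this endpoint at all.
- Summing planned, unplanned and PEx-hospitalization rows does not give the total. The sum misses the categories with no row. It can also count twice a planned antibiotic admission that meets the PEx definition, because nothing in the SAP makes those rows exclusive.
- The unplanned row does not repeat the restriction to CF. It stands under a CF-related heading, so this is an ambiguity only.

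**Annualization.** The 48 weeks is a stated convention (2 × 24 weeks), so there is no derived figure to reproduce. The comparison needs a year length. I take 52 weeks as the lower value and 365.25/7 = 52.179 weeks as the upper. The second uses the days-to-years divisor that SAP Appendix A applies to age ("age at informed consent/assent (in days)]/365.25").

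- 48 weeks in days: 48 × 7 = 336; 365.25 − 336 = 29.25 days short.
- Shortfall against 52 weeks: 1 − 48/52 = 7.7%.
- Shortfall against 52.179 weeks: 1 − 48/52.179 = 8.0%.
- Equivalently, calendar-year values are higher by 52/48 − 1 = 8.3% to 52.179/48 − 1 = 8.7%.

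Illustration, assuming a subject with 10 event days:

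| Weeks on study | SAP factor (48) | 52 weeks | 52.179 weeks |
|---|---|---|---|
| 24 | 10 × 48/24 = 20.0 | 10 × 52/24 = 21.7 | 10 × 52.179/24 = 21.7 |
| 169/7 = 24.143 (period ends on Day 169) | 10 × 48/24.143 = 19.9 | 10 × 52/24.143 = 21.5 | 10 × 52.179/24.143 = 21.6 |

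Event counts and unscaled days are not affected.

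**The case against.** On coverage, the missing category is narrow: unplanned, at least 24 hours, for sinopulmonary antibiotics, and below the sign threshold. With about 56 children followed for 24 weeks, nothing in the documents shows that even one such admission is expected. The events are not lost either. Protocol 11.4.6.2 requires safety reporting for any hospitalization, an inpatient admission for an adverse event is serious under protocol 13.1.2.1, and SAP 9.4.1 tabulates and lists serious events. The protocol also never asks for a total.

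On annualization, the 48-week factor is stated openly, multiplies every subject by the same constant in a single-arm study, and can be converted exactly. The endpoint names a number of events, so annualized duration is an addition of the SAP. The 365.25 divisor in Appendix A serves age, not event rates.

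Most of this stands as a limit on consequences. It does not supply the endpoint. The adverse event tables count subjects by preferred term, not CF admissions or days. They also cover a different period: the treatment-emergent period of SAP 9.1 ends no later than 28 days after the last dose. The PEx period runs to Week 24, and protocol 9.1.4 keeps subjects who stop treatment early in follow-up. A reader would have to count from listings. The point about age is fair, which is why the shortfall is also given against a plain 52-week year; 48 weeks is short of either.

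**Conclusion.** Both parts hold, and both should be corrected before the Part B tables are produced.

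The planned output for a named secondary endpoint is incomplete: unplanned sinopulmonary-antibiotic admissions with fewer than 4 signs are in no row, and no total exists or can be derived. This rests on the literal wording of SAP 9.3.2.2.2. The number of admissions affected cannot be estimated from the documents.

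The annualized durations are 7.7% to 8.0% below a calendar-year value, with the year taken as 52 to 52.18 weeks. Because the factor is disclosed, this is a mislabelled scale and not a hidden error.

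The consequences are limited. The summary is descriptive, no test or primary safety conclusion depends on it, and the omitted admissions would generally be found among the serious adverse events.

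**What to change.** In SAP 9.3.2.2.2:

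1. Add the total number and total days of all CF-related hospitalizations of at least 24 hours, whether or not PEx criteria are met, counting each admission once.
2. Break that total down by planned/unplanned and by antibiotic/other reason. This also gives a place to planned CF admissions for reasons other than antibiotics.
3. State that the PEx-hospitalization rows may overlap with this total and are not to be added to it.
4. Restrict the unplanned row explicitly to CF.
5. Replace 48 weeks with 52.18 weeks (365.25/7), or keep 48 and label the result as per 48 weeks.

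The cost is SAP wording and table programming. Dates and reasons for admission are already collected under protocol 11.4.6.2, so no new data are needed.
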